### 2.5.2 Exclusion Criteria – HIV-negative Subjects

A person who meets *any* of the following exclusion criteria will *not* be enrolled in the study:

- 1. Is nursing;
- 2. Has body weight <50 kg;

**Confidential and Proprietary** 

[name] 5/31/15 10:25 AM Deleted: Table 2-3. Schedule of Study

[name] 5/31/15 10:25 AN

Deleted: Table 2-2. Schedule of Study

Events - Screening Through Day 74

Events – Dose #3 to End-of-Study Visit

[name] 5/31/15 10:25 AM Deleted: 15.3 [name] 5/31/15 10:26 AM Formatted: Font:Bold

[name] 5/31/15 10:26 AM Formatted: Font:Bold [name] 5/31/15 10:25 AM Deleted: 8.3 [name] 5/31/15 10:25 AM Deleted: 8.3 [name] 5/31/15 10:26 AM Formatted: Font:Bold

- 3. Has a history of active tuberculosis;
- 4. Has previously received another investigational vaccine against tuberculosis;
- 5. Has received any investigational drug during the prior three (3) months;
- 6. Has had surgery requiring general anesthesia during the prior three (3) months;
- 7. Has lost >500 ml of blood (by any process, including donation) during the prior three (3) months;
- 8. Has received systemic immune suppressive or stimulatory prescription drugs during the prior three (3) months;
- 9. Has participated in any biomedical research protocol during the prior one (1) month;
- Has used any prescription or over-the-counter medication during the prior one (1) month, unless approved by both the Investigator and the Sponsor;
- 11. Has had an illness consistent with acute viral or bacterial infection within the prior (2) two weeks;
- 12. If IGRA-positive, has a chest x-ray with any findings consistent with active tuberculosis;
- 13. Has a positive test for hepatitis B surface antigen (HBsAg) or for antibody to hepatitis C virus (HCV) [HIV-negative subjects only; HIV-positive subjects are not excluded for prior hepatitis B or C]
- 14. Has confirmed results on a screening laboratory test (hematology, coagulation, chemistry, urinalysis) that represent Grade 1 or greater abnormalities (tests with abnormalities may be repeated once);
- 15. Has a calculated creatinine clearance of <80 mL/min (based on the Cockcroft-Gault equation);
- 16. Has, within the past 10 years, had evidence of or required treatment for cancer (except treated basal or squamous cell carcinoma of the skin, or cured cervical carcinoma-in-situ);
- 17. Has other significant medical disease (chronic or active within the past 6 months), including, but not limited to: cardiac disease (e.g., unstable angina, myocardial infarction, congestive heart failure, ventricular arrhythmia), uncontrolled seizure disorder, liver disease, autoimmune or antibody-mediated diseases (e.g., lupus, rheumatoid arthritis), organ transplantation, chronic infection, uncontrolled diabetes; diseases judged by the Investigator as not clinically significant or as fully resolved will be reviewed with the Medical Monitor;
- 18. Has clinically significant abnormal findings on vital signs or physical examination;
- 19. Is expected to have surgery requiring general anesthesia during the study period;
- 20. Is, in the judgment of the Investigator, not suitable to participate in this clinical study.

### 2.5.3 Additional / Alternative Inclusion Criteria for HIV-positive Subjects

- 1. Has a previously documented positive HIV-1 viral load;
- 2. Has been on a stable combination anti-retroviral therapy (ART) for the past three (3) months;
- 3. Has been enrolled in regular HIV care for the past year, including a documented clinic visit within the past eight (8) months.
- 4. If IGRA-positive, has completed prophylaxis for latent TB, has a contraindication to prophylaxis, or has refused prophylaxis treatment.

#### 2.5.4 Additional / Alternative Exclusion Criteria for HIV-positive Subjects

- 1. Has a history of an AIDS-defining opportunistic infection;
- 2. Has had a CD4 count <200/uL at any time in the past year;
- 3. Has confirmed results on a screening laboratory test (hematology, coagulation, chemistry, urinalysis) that represent Grade 2 or greater abnormalities (tests with abnormalities may be repeated once).

# 2.6 Treatments

All treatments will be administered as scheduled by intradermal injection in the deltoid.

# 2.6.1 Investigational Treatment

Different doses of DAR-901 (see Table 2-1) administered in a dose volume of 0.1 mL (see Section 9.5).

[name] 5/31/15 10:25 AM Deleted: Table 2-1

### 2.6.2 Comparator treatment

Active comparator: Tice BCG, Organon, Teknika, 1-8x10^6 organisms in 0.1 mL. Inactive comparator: 0.1 mL of Sterile Saline for Injection (placebo).

#### 2.7 Assessments

# 2.7.1 Safety Assessments

The safety and tolerability of DAR-901 will be assessed using reported and observed adverse events and scheduled safety observations, including quantitative measurements of injection site reactions, digital photography of injection site reactions, patient-recorded temperatures, vital signs, physical examination, laboratory tests (hematology, chemistry, and coagulation), urinalysis.

# 2.7.2 Immunogenicity Assessments

The following assays will be performed using isolated fresh or fresh frozen peripheral blood mononuclear cells (PBMCs) or serum, as indicated, using antigens prepared in the laboratory and previously used in non-clinical immunogenicity studies. Additional assays may be developed and applied as long as the blood volume required does not exceed that specified in Table 2-4.

- Antigens:
  - Standard: DAR-901 sonicate; MTb lysate; Ag 85, ESAT
  - Exploratory: mycobacterial peptides specific to DAR-901 and BCG
  - Controls: positive (PHA, PMA/ionomycin, or SEB as appropriate); negative (saline or media).
- Assays primary:
  - Antigen-specific IFN-γ production by PBMCs in vitro by IFN-γ ELISA (Dartmouth)
  - IFN- $\gamma$  Elispot PBMCs stimulated with antigen and assessed for IFN- $\gamma$  secreting cells
  - (Aeras)
- Assays additional:
  - Serum antibody to lipoarabinomannan (LAM) by ELISA (Dartmouth)
  - Antigen-specific 17-color intracellular cytokine staining (ICS) assay (Aeras)
  - RNA expression assay (Aeras)
  - Mycobacterial growth inhibition assay (MGIA) on PBMCs (Aeras)

# 2.8 Statistical Analyses

#### 2.8.1 Analysis Populations

Within each population (HIV-negative and –positive), analyses will be performed comparing subjects by dose level and by treatment assignment (DAR-901 vs. Placebo). Where appropriate, data for different dose levels may be pooled.

- Safety Population all subjects who received at least one injection of study medication.
- *Immunogenicity Populations* all subjects with evaluable immunogenicity data, based on protocol compliance, adequate numbers of samples, and successful sample assays.

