#### 2.4 Study Design

This is a Phase 1, randomized, controlled, double-blind, multiple-dose, dose-ranging study of DAR-901 to be conducted in HIV-negative and HIV-positive adults previously vaccinated with BCG. The goals of the trial are to determine the safety, tolerability, and immunogenicity of multiple doses of the vaccine at different dose levels, ranging from 0.1 to 1 mg. The maximum dose level (1 mg) corresponds to the dose of SRL 172 used in the successful DarDar trial. A dose of 0.3 mg DAR-901 provided maximal immunogenicity in mice; the 0.1 mg dose is included to provide further dose response data and assure a safe starting dose level.

Doses will be administered by intradermal injections in the deltoid area at 0, 2, and 4 months (Day 1, Day 53-67, and Day 113 to 127, respectively). In the Phase 2 study of SRL 172 conducted in Finland, this regimen showed significant immunogenicity. The intervals between injections and route of administration are consistent with all previous studies of SRL 172.

Table 2-1, displays the dose groups by HIV status and dose level (mg) per injection. All cohorts include placebo (saline) controls; in addition, the HIV-negative cohorts (A1–A3) include positive controls (a single dose of BCG as Dose #3, with saline at preceding doses).

[name] 5/31/15 10:25 AM **Deleted:** Table 2-1

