#### Table 2-1. Dose Groups by HIV Status, IGRA status, and Dose Level

Dose	HIV	IGRA	DAR-901		BCG	Placebo	Total
Group	Status	status	(Dose Level)	(N)	(N)	(N)	
A1	Neg	Neg	0.1 mg	10	3	3	16
A2	Neg	Neg	0.3 mg	10	3	3	16
A3	Neg	Neg	1 mg	10	3	3	16
A4	Neg	Pos	TBD	4-6*	-	0	4-6
B1	Pos	Neg	TBD	5-8*	_	-	5-8
B2	Pos	Pos	TBD	5-8*	-	-	5-8
Total				44-52	9	9	62-70*

TBD, to be determined. The dose level will be selected based on the preceding experience within the protocol as detailed in text.

\* Ranges represent minimum and maximum number of subjects per cohort.

All subjects will be screened by Interferon-gamma release assay (IGRA; QuantiFERON®-TB Gold, Cellestis) for evidence of latent TB infection (LTBI). IGRA-positive subjects will be excluded from the initial dose escalation cohorts (A1–A3).

Based on the results obtained in the HIV-negative dose-escalation, a target dose level will be selected and administered to one additional HIV-negative cohort:

• Cohort A4: HIV-negative, IGRA-positive subjects; open label.

In addition, the protocol provides for administering the target dose to two cohorts of HIV-positive subjects, contingent on assessment of the vaccine's safety, tolerability and immunogenicity in the HIV-negative cohorts and the availability of resources:

• Cohort B1: HIV-positive, IGRA-negative subjects; open label.

• Cohort B2: HIV-positive, IGRA-positive subject; open label.

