### 9.6 Method of Assigning Patients to Treatment Groups

The first subject in dose group will be assigned active treatment (DAR-901)(see Section 2.4.1). For subsequent subjects within the dose group treatment will be assigned by computer-generated randomization for A1-A3 and open label for A4, B1 and B2. Suitable randomization procedures will be established by the CRO data management and clinical services performing the protocol and approved by the Sponsor. The research pharmacist will be provided a list of treatment assignments.

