### 14.3 Statistical Methods

Study results will be analyzed using descriptive statistics. Adverse events will be listed per dose level and analyzed by intensity and relationship to investigational product. All other variables will be analyzed descriptively per dose level. No formal statistical comparisons are planned.

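### Section 2.8.1 plans placebo and dose-level comparisons that the HIV-positive cohorts cannot supply, and grouping by dose level would mix open-label IGRA-positive A4 with a randomised IGRA-negative cohort

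*Protocol*

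**What the plan says.** **Planned comparisons.** Section 2.8.1 opens "Within each population (HIV-negative and –positive") and then states that "analyses will be performed comparing subjects by dose level and by treatment assignment (DAR-901 vs. Placebo"). It adds: "Where appropriate, data for different dose levels may be pooled". IGRA status is not named. Section 14.2 repeats the dose-level comparison within the safety and immunogenicity populations, and mentions neither placebo, HIV status nor IGRA status. Section 14.3 lists adverse events by dose level, rules out formal comparisons, and says: "All other variables will be analyzed descriptively per dose level". Section 14.5 allows further analyses by HIV and latent-TB status, but as an option and for immunogenicity only.

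**Design.** Section 2.4 states: "All cohorts include placebo (saline) controls". Table 2-1 shows otherwise. The A4 row reads "A4 Neg Pos TBD 4-6* - 0 4-6", and the B1 and B2 rows have dashes for both BCG and placebo. The text below the table makes all three cohorts open label, for example "Cohort B1: HIV-positive, IGRA-negative subjects; open label". Section 9.6 confines randomisation to A1-A3. Within those cohorts, "The first subject in dose group will be assigned active treatment (DAR-901").

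**Dose.** Under 2.4.1, A4 receives the 1 mg level if the Dose Review Committee finds it safe, and otherwise the A1 or A2 level. B1 and B2 receive the same dose as A4.

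**Blinding.** Section 7.3 describes the study as randomised, placebo-controlled and double-blind, and excepts only the first subject.

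**The concern.** An analysis section should ask only for contrasts that the design can deliver. In the HIV-positive stratum, 2.8.1 asks for two that do not exist. Whoever programs the tables must either leave them empty or borrow a control group from the HIV-negative stratum, which the protocol does not provide for.

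In the HIV-negative stratum the problem is what gets grouped together. Safety is the primary objective, and descriptive tables are the only means of reading it. If the table unit is dose level alone, the level that A4 receives combines two kinds of subject: blinded, randomised, IGRA-negative subjects, and unblinded, uncontrolled, IGRA-positive subjects. A difference between that level and the others could then reflect IGRA status or open-label reporting rather than dose. The protocol itself keeps IGRA-positive subjects out of A1-A3, stratifies by IGRA under risk management (2.4.2.1), and argues in 7.3 that blinding protects adverse-event assessment.

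**Working it through.** **Inputs** (Table 2-1, 2.4.1, 9.6):

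| Cohort | HIV | IGRA | Allocation | DAR-901 | BCG | Placebo |
|---|---|---|---|---|---|---|
| A1 | neg | neg | randomised after first subject | 10 | 3 | 3 |
| A2 | neg | neg | randomised after first subject | 10 | 3 | 3 |
| A3 | neg | neg | randomised after first subject | 10 | 3 | 3 |
| A4 | neg | pos | open label | 4-6 | none | 0 |
| B1 | pos | neg | open label | 5-8 | none | none |
| B2 | pos | pos | open label | 5-8 | none | none |

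**Step 1. Reproduce the plan's totals.**
- DAR-901 minimum: 10 + 10 + 10 + 4 + 5 + 5 = 44. Maximum: 10 + 10 + 10 + 6 + 8 + 8 = 52.
- BCG: 3 × 3 = 9. Placebo: 3 × 3 = 9.
- All subjects: 44 + 9 + 9 = 62 to 52 + 9 + 9 = 70, as in Table 2-1.
- Maximum DAR-901 exposure: 30 + 6 = 36 HIV-negative and 8 + 8 = 16 HIV-positive, as in 7.4.

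**Step 2. HIV-positive stratum.**
- DAR-901: 5 + 5 = 10 to 8 + 8 = 16. Placebo: 0.
- Dose levels: one, because B1 and B2 both take the A4 dose.
- Neither the placebo comparison nor the dose-level comparison of 2.8.1 can be formed.

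**Step 3. HIV-negative stratum, by dose level.**
- A4 takes the level of A3, or else that of A1 or A2, so it always shares a level with an IGRA-negative cohort of 10 on DAR-901.
- IGRA-positive share at that level if A4 takes the A3 dose: 4/(10 + 4) = 28.6% to 6/(10 + 6) = 37.5%. The fraction is the same for A1 or A2, since each also has 10 on DAR-901.

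**Step 4. HIV-negative stratum, DAR-901 versus placebo.**
- DAR-901: 30 + 4 = 34 to 30 + 6 = 36. Placebo: 9.
- IGRA-positive share of the DAR-901 side: 4/34 = 12% to 6/36 = 17%. Share of the placebo side: 0/9, because IGRA-positive subjects are excluded from A1-A3.
- A4 therefore has no IGRA-positive placebo control, randomised or otherwise.

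**Step 5. What remains comparable.**
- Limited to A1-A3: 30 DAR-901 versus 9 placebo, all HIV-negative and IGRA-negative.
- Of the 30, 3 are open-label first subjects (one per cohort), so 30 - 3 = 27 were randomised.

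The protocol bases no sample size on power, so no power or error-rate calculation applies.

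**The case against.** The best defence is that no sentence orders A4 to be merged with A3. Table 2-1 defines dose groups by HIV status, IGRA status and dose together. Section 14 leaves population definitions and data-handling conventions to a separate SAP, which was not available, and the layout of descriptive tables is ordinary SAP content. This has force: the mixing follows from grouping by dose level as written, and a SAP could prevent it. But a SAP cannot supply a placebo arm or a second dose for B1 and B2, and it cannot make the placebo sentence in 2.4 true. Section 14.5 covers latent-TB status only optionally and not for safety.

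The defence is also right on consequence. The analyses are descriptive. Escalation and dose selection rest on A1-A3, and Table 2-5 puts the dose safety review at week 26 and the first A4 dose at week 27.

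A reader might infer more than the text supports:

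- *That all HIV-positive and HIV-negative recipients of the target dose would be summarised as one group.* Section 2.8.1 already separates the HIV strata. Sections 14.2 and 14.3 are looser, but nothing says that they override it.
- *That calendar time and blinding distort only the target dose.* A1-A3 are dosed in sequence (weeks 1, 4 and 7 in Table 2-5), so dose is tied to calendar time throughout, and each has an open-label first subject. Randomisation is within a cohort, never between doses. Restricting to A1-A3 removes the IGRA mixture but does not make dose a randomised contrast.
- *That the SRL 172 abscesses show a higher risk in IGRA-positive subjects.* The cases in Tables 5-4 and 5-5 were in HIV-positive recipients, and the risk features noted were prior TB or apical scarring. That is not latent infection by IGRA, and 2.5.2 excludes a history of active TB. The documents give no reaction rate by IGRA status, so the size of any distortion cannot be estimated.
- *That the open-label first subjects should be dropped.* The safety population is everyone dosed, and 7.3 explains the first-subject rule. Showing 27 versus 9 is a preference, not a correction.

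**Conclusion.** The point holds. It should be fixed, but it does not threaten the trial's conduct or its dose decisions.

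Two parts follow directly from the text. In HIV-positive subjects both comparisons planned in 2.8.1 are impossible (10-16 versus 0, one dose level). The placebo statement in 2.4 is contradicted by Table 2-1, and the double-blind description in 7.3 does not fit three of the six cohorts. The third part is conditional: if summaries follow dose level as 2.8.1, 14.2 and 14.3 word it, 29-38% of the level that A4 shares will be open-label IGRA-positive subjects with no matching control.

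This rests on the planned cohort sizes in Table 2-1, on A4 taking a level already used in A1-A3 as 2.4.1 provides, and on Part B being opened, which depends on the safety review and on resources. If Part B is not opened, the HIV-positive comparisons are moot rather than feasible.

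**What to change.** 1. In 2.8.1, 14.2 and 14.3, make the cohort (dose × HIV × IGRA) the unit of summary.
2. Limit DAR-901 versus placebo and dose-level comparisons to A1-A3: 30 versus 9 in the safety population, with a note that 3 of the 30 are open-label first subjects.
3. Describe A4, B1 and B2 separately as uncontrolled open-label cohorts, using within-subject change. For B1 and B2 the scheduled immune assays (baseline and Day 56 after Dose 3) allow this.
4. Reconcile the placebo statement in 2.4 and the double-blind statement in 7.3 with Table 2-1, so that both refer to A1-A3.

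The cost is protocol wording, carried into the SAP. No new data, visits or subjects are needed.

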#### 2.8.2 Safety Analyses

Tabulation and descriptive statistics of adverse events, vital signs, physical examinations, and laboratory tests.

#### 2.8.3 Efficacy Analyses

Not applicable

#### 2.8.4 Immunogenicity Analyses

Data will be analyzed using descriptive statistics and graphical displays.

[name] 5/31/15 10:25 AM **Deleted:** Table 2-4

# 2.8.5 Determination of Sample Size

The size of the study is based on prior experience with Phase 1 vaccine studies and represents the number of patients that will permit preliminary evaluation of safety and tolerability (primary objective) and, thereby, support the advancement of the vaccine development program.

# 2.9 Schedules of Study Events

Table 2-2. Schedule of Study Events – Screening Through Day 74

Event / Evaluation  Dose #			#1							#2				
Day 	≤-28		1		+3 	+5 	+7 ⁵	+10 to		53-67	7	+3,54	+7	+10 to
Hour		Pre	0	1	]			+28 	Pre	0	0.5			+28 
Informed Consent	Х													
Medical History	Х													
Physical examination 	Х	Х												
Vital signs	Х	Х		Х	$X^3$		Х		Х		Х		Х	
Injection Site Assessment 					X3		Х		Х				Х	
Phone Contact					Х	Х		Х				Х		Х
Safety Laboratory Tests	Х	X 							Х					
HIV Monitoring Tests 	Х	X 							Х					
Urinalysis	Х								Х					
Pregnancy test (F only)	Х	Х							Х					
IGRA test, Chest X-ray 	Х													
Serology 	Х													
Immunogenicity Studies		X 							Х					
Dose administration			Х							Х				
Monitoring AE & Con Med		From Screening to End of Study Visit												

 "+7" indicates visit to be performed 6 to 8 days after actual day of dosing.

 Physical exam includes weight and, at screening only, height.

<sup>1 For details of study evaluations see Section 10.

<sup>2 Day is relative to the calendar day of the first injection of study drug, designated Day 1; time (Hour) is relative to time of injection, designated 0 hr. "Pre" indicates within 2 hr prior to injection.

 $\frac{3}{4}$  Day 3 visit only for first subject in each cohort. All other subjects will be contacted by phone on Day 3.

<sup>4 "+3", "+5", "+10 to +28" – indicates phone contacts for adverse event monitoring, including injection site

reactions, to be performed on days 3 and 5 post-dosing and at least twice weekly through day 28 post-dosing.

<sup>7 Assessment of injection site area comprises a structured examination of the injection site and measurements of any reaction (see Section 12.5).

<sup>8 HIV monitoring tests – HIV viral load, CD4 counts; to be performed only on HIV-positive subjects

<sup>9 IGRA will be performed on all subjects. All IGRA positive subjects will have a chest x-ray; see Section 2.4.2 for provisions regarding preventive therapy in those subjects.

<sup>10 Serology includes hepatitis B surface antigen, antibody to hepatitis C virus, and antibody to HIV-1 and -2; see Section 10.3.3 for details.

#### Table 2-3. Schedule of Study Events - Dose #3 to End-of-Study Visit

Event / Evaluation  D	ose#		#3							EOS 
E	Day 		113-127	,	+3,5 	+7 	+10 to +28 	+28 	[contact]
I	Hour	Pre	0	0.5	-					
Informed Consent										
Medical History										
Physical examination 		Х						Х		
Vital signs		Х		Х		Х		Х	Х	Х
Injection Site Assessment	17		1			Х		Х	Х	Х
Phone contact					Х		Х			
Safety Laboratory Tests		Х						Х		
HIV Monitoring Tests 		Х						X		
Urinalysis								Х		
Pregnancy test (females o	nly)	Х						X		
IGRA test, Chest X-ray									(X) 	X 
Serology										
Immunogenicity Studies		Х				Х		Х	X 	Х
Dose # administration			Х							
Monitoring AE & Con Med				F	From Scr	eening	to End of S	Study Vi	sit	

 Physical exam includes weight and, at screening only, height.

-  HIV monitoring tests HIV viral load, CD4 counts; to be performed only on HIV-positive subjects
-  Immune assays for HIV positive subjects are only performed at baseline and at Day 56 after dose #3
-  Labs not repeated if subject dosed within 2 weeks of screening and has no intervening change in health status IGRA repeated at Day 56 or EOS visit for subjects in cohort A3 (3 mL blood)

<sup>11 For details of study evaluations see Section 10.

<sup>12 EOS, End-of-Study visit

<sup>13 Day is relative to the calendar day of the first injection of study drug, designated Day 1; time (Hour) is relative to time of injection, designated 0 hr. "Pre" indicates within 2 hr prior to injection.

<sup>14 "+3", "+5", "+10 to +25" – indicates phone contacts for adverse event monitoring, including injection site reactions, to be performed on days 3 and 5 post-dosing and at least twice weekly between the visits scheduled for days 7 and 28 post-dosing.  "+7", "+28", "+56" indicate visits to be performed 6 to 8 days, 26 to 30 days, and 54 to 60 days, respectively,

after actual day of dosing.

<sup>17 Assessment of injection site area comprises a structured examination of the injection site and measurements of any reaction (see Section 12.5).

Table 2-4. Estimation of Blood Volumes Required

Event Day /Evaluation 	Vol (mL)	Scrn	1	53-67	113-127	+7	+28	+56	EOS 293-307	Approx Total Vol (mL)
Dose #			#1	#2	#3					
Safety Lab Tests	15	Х	Х	Х	Х		х		Х	78
HIV Monitoring Tests	10	Х	Х	х	Х		х			50
Pregnancy test (F only) 		Х	Х				х			0
Immunogenicity (cells)	40		Х	Х	Х	Х	X	Х	Х	280 
Immunogenicity (serum)	5		Х	х	Х	Х	х	Х	Х	35 
RNA expression	3		Х	х		Х			Х	12
Serology (Hep B, C, HIV)	10	Х								10
Total mL blood drawn		35	73	73	70	48	70	45	51	465 

 <sup>19 The volumes shown are estimates; final volumes may vary, but will not be more than 15% greater than shown.
  For details of study evaluations see Section 10.
  Pregnancy test does not require additional blood volume.
 Limit of two immunogenicity assays for HIV positive subjects in cohorts B1 and B2 reduces total volume of phlebotomy by 225 mL to 237 mL

DAR-901	
Protocol DAR-901-MDES, Version 4.1	

Page 14 of 75 Date: 30 March 2015

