RNA transcriptional analysis is an exploratory assessment at this time. It offers the potential to assess changes in the expression of genes related to both innate and adaptive immunity and to identify the activation of specific intracellular pathways.

The mycobacterial growth inhibition assay (MGIA) is currently being developed by Aeras with the potential for qualification as a new method to directly assess the ability of PBMCs to inhibit mycobacterial growth. Assays from all 6 timepoints will be conducted at the same time on frozen PBMCs.

Page 45 of 75 Date: 30 March 2015

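### Table 2-3 footnote 19 and Table 2-4 contradict each other on RNA sampling in HIV-positive subjects: one baseline tube on one reading, four tubes on the other

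*Protocol*

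**What the plan says.** Four places in the protocol bear on this.

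- **Tables 2-2 and 2-3.** The visit schedules have one row for immunogenicity studies and no row for RNA. In that row, marker 19 sits on the Day 1 and Dose #3 +56 visits. The footnote reads: "Immune assays for HIV positive subjects are only performed at baseline and at Day 56 after dose #3".
- **Section 2.7.2 and Table 10-5.** Both list RNA expression among the immunogenicity assays. Table 10-5 gives its purpose as defining changes in gene expression. The comments in section 10.5.1 call it exploratory and add: "It offers the potential to assess changes in the expression of genes related to both innate and adaptive immunity".
- **Table 2-4.** RNA has its own row, separate from the immunogenicity rows for cells and serum. It is 3 mL per draw at Day 1, Day 53-67, Dose #3 +7 and end of study, 12 mL in all.
- **Footnote 22 to Table 2-4.** It states: "Limit of two immunogenicity assays for HIV positive subjects in cohorts B1 and B2 reduces total volume of phlebotomy by 225 mL to 237 mL". Marker 22 is attached to the cells total, the serum total and the grand total, but not to the RNA total.

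**The concern.** The visits that footnote 19 allows (baseline and +56) and the visits at which Table 2-4 draws RNA share only Day 1. If footnote 19 governs RNA, each HIV-positive subject gives one baseline sample for an assay whose stated purpose is change. If it does not, Table 2-4 budgets three further RNA draws in these subjects at visits where footnote 19 says no immune assays are done.

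Site staff must follow one of the two, and the protocol does not say which. A SAP cannot settle this afterwards, because a tube that was not drawn cannot be analysed. Section 7.3 gives a possible difference in immune response as the reason for enrolling both HIV-negative and HIV-positive adults. The loss would fall on the HIV-positive side, where each cohort has only 5 to 8 subjects.

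**Working it through.** **Inputs** (Table 2-4, mL per draw): safety 15, HIV monitoring 10, cells 40, serum 5, RNA 3, serology 10. Table 2-3 footnote 21 gives 3 mL for a repeat IGRA in cohort A3 only.

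**Step 1. Reproduce the plan's column totals**, to rule out a misaligned table. The stated row is "Total mL blood drawn 35 73 73 70 48 70 45 51".

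| Visit | Sum | mL |
|---|---|---|
| Screening | 15+10+10 | 35 |
| Day 1 | 15+10+40+5+3 | 73 |
| Dose #2 | 15+10+40+5+3 | 73 |
| Dose #3 | 15+10+40+5 | 70 |
| +7 | 40+5+3 | 48 |
| +28 | 15+10+40+5 | 70 |
| +56 | 40+5 | 45 |
| End of study | 40+5+3+3 | 51 |

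The sum is 465, as stated. The second 3 mL at end of study comes from the safety row, whose total of 78 equals 5×15+3. I take it to be the A3-only IGRA. The +56 column is cells and serum alone, so there is no RNA tube at Day 56.

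**Step 2. Reproduce footnote 22.** Cells and serum are drawn at seven visits. Keeping two omits five: 5 × (40+5) = 225 mL, the stated reduction. Removing the A3-only IGRA as well gives 465 − 3 − 225 = 237 mL, the stated remainder. By component for an HIV-positive subject:

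- safety 5×15 = 75
- HIV monitoring 5×10 = 50
- serology 10
- cells 2×40 = 80
- serum 2×5 = 10
- RNA 4×3 = 12

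75+50+10+80+10+12 = 237. All four RNA tubes are in that figure.

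**Step 3. Volumes under each reading.** Without RNA the components sum to 225 mL.

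| RNA in B1/B2 | Volume, mL | Post-vaccination RNA samples |
|---|---|---|
| Four tubes, as in the Table 2-4 row | 225+12 = 237 | 3 |
| Baseline only, literal footnote 19 | 225+3 = 228 | 0 |
| Baseline plus an added +56 tube | 225+6 = 231 | 1 |

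The stated 237 mL does not match literal footnote 19, which would need 228 mL.

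**Step 4. Number affected.** Table 2-1 plans 5-8 subjects in B1 and 5-8 in B2, so 10 to 16 in all.

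**The case against.** The strongest objection is that the protocol does provide for RNA change in these subjects. RNA has its own row in Table 2-4, marker 22 is not on that row, and both the 225 mL reduction and the 237 mL remainder fit a limit on cells and serum only. On that reading B1 and B2 have a baseline and three later RNA samples. This stands against any claim that RNA change cannot be derived in HIV-positive subjects, which a reader might infer from footnote 19 alone. It does not remove the conflict: the footnote is categorical, RNA is classed as an immune assay, and the visit schedules give it no other row.

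The volume evidence has limits too. 465 − 225 is 240, so 237 needs the inference that the A3-only IGRA was removed. Footnote 22 could also be read as a reduction ranging from 225 to 237 mL, whose upper end (225+12) would drop every RNA tube. Table 2-4 labels its volumes as estimates.

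A reader might also infer that RNA must be drawn at the same visit as the IFN-γ assays. The protocol sets no such requirement, and RNA is absent at +56 in every cohort. Nor does A4 need an extra tube: footnote 19 does not restrict it, it already has the four RNA visits, and as an IGRA-positive cohort it matches only B2.

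Finally, the stake is modest. RNA is an additional, exploratory assay, and no formal hypothesis testing is planned. The secondary objective emphasises IFN-γ secretion and ELISpot, both of which keep baseline and Day 56 samples.

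**Conclusion.** The contradiction is real and should be resolved before B1 and B2 are sampled. Under literal footnote 19, each HIV-positive subject has one RNA tube and no change from baseline. Under the most natural reading of footnote 22, each has four, three of them at excluded visits. The documents do not decide between the two, so it is not established that RNA change is lost, only that one stated rule would lose it.

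The size is all 10 to 16 planned HIV-positive subjects, if both cohorts are enrolled; section 2.4.1 makes that contingent on the safety review and resources. The consequence is confined to an exploratory assay, and no primary, safety or main immunogenicity result changes. The volume argument rests on treating the extra 3 mL at end of study as the A3-only IGRA. The absence of an RNA tube at +56 does not depend on that assumption.

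**What to change.** Reconcile footnote 19 of Table 2-3 with Table 2-4 so that B1 and B2 have at least one post-vaccination RNA sample. Either route does this.

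- **(a) Limit footnote 19 to cells and serum.** State that RNA in HIV-positive subjects stays at Day 1, Dose #2, Dose #3 +7 and end of study, as in the HIV-negative cohorts. The 237 mL in footnote 22 stands, and the RNA visits remain shared across populations. The cost is one sentence, with no blood beyond what Table 2-4 already budgets.
- **(b) If the limit is meant to cover RNA, add a 3 mL RNA tube at Dose #3 +56 for B1 and B2** and restate footnote 22 as leaving 231 mL (a reduction of 462 − 231 = 231 mL, where 462 is 465 less the A3-only IGRA). The +56 draw rises from 45 to 48 mL (3/45 = 6.7%), within the table's 15% allowance. The cost is one added tube and assay per subject. The downside is that B1 and B2 would then share no post-baseline RNA visit with the HIV-negative cohorts.

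Under either route, word footnote 22 so that the reduction and the remaining volume cannot be read as a range.
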